4.3 Discontinuation of Study Treatment and Subject Withdrawal

4.3.1 Discontinuation of Study Treatment

Subjects may discontinue study treatment with CSL312 at any time at their own request, or at the discretion of the investigator or CSL for safety, behavioral, or administrative reasons.

Subjects who discontinue treatment with CSL312 will be encouraged to remain in the study until Day 182 in order to collect study assessments. Refer to Section 4.3.2 for details on handling subject withdrawals.

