10.3.3 Safety Analyses

Safety data will be summarized using the safety analysis set.

Adverse events with a start date and time occurring after the first administration of the study drug will be considered treatment-emergent AEs (TEAEs). Adverse events with missing or partial start date or time will also be considered TEAEs following the worst-case principle unless the partial data clearly indicates that the AE started before first administration date and time.

Treatment-emergent AEs occurring until the Follow-up Visit will be summarized. Only TEAEs will be included in analysis, although all AEs will be listed.

The following tables will be presented for AEs occurring at any dose:

- Summary of subjects with AEs (number with any AE, with AEs occurring within 24 hours of investigational product injection, with SAE, with related AE, with AEs leading to study discontinuation, with each intensity, and with each outcome).
- Summary of subjects with SAEs (number with any SAE, with SAEs occurring within 24 hours of investigational product injection, with related SAE, with SAEs leading to study discontinuation, with each intensity, and with each outcome).
- Incidence of subjects with AEs by SOC and PT.
- Incidence of subjects with SAEs by SOC and PT.
- Incidence of subjects with AEs by severity and SOC and PT.

- Incidence of subjects with AEs by relationship to investigational product and SOC and PT.
- Incidence of subjects with AEs leading to discontinuation by SOC and PT.
- Incidence of subjects with TEEs by SOC and PT.
- Incidence of subjects with bleeding events by SOC and PT.
- Incidence of subjects with severe hypersensitivity / anaphylaxis by SOC and PT.
- The number of subjects experiencing AEs which occur in at least 1 treatment in at least 1, 2, 3, 4, and 5% of events will also be presented.
- Laboratory findings reported as AEs.

Summaries will include the number and percentage of subjects, the number of AEs, and the number of AEs per injection and per subject year (where applicable).

A summary of non-serious AEs only will be presented by treatment and also by SOC, PT, and treatment.

Summaries of ISRs will be presented by treatment and also by MedDRA SOC and PT, and treatment, with relationship to investigational product and with severity.

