Subjects who experience either study treatment discontinuation or study discontinuation due to COVID-19 will have the reason captured in the eCRF. On the appropriate eCRF form for study discontinuation (“Conclusion of Subject Participation” form) or eCRF form for treatment discontinuation (“End of Treatment” form) as reason ‘Pandemic Related’ can be selected. Cases of study treatment discontinuation or study discontinuation due to pandemic will be included in the summary of subject disposition.

Adverse Events

Adverse events associated with COVID-19, which can include a clinically significant laboratory finding like a positive test result for COVID-19, will be reported by investigators. COVID-19 associated adverse events are identified via MedDRA coding. Relevant adverse events will be identified for reporting by the following Standardised MedDRA Query (SMQ): COVID-19 (SMQ). All COVID-19 associated adverse events will be included in standard AE tables.

An overview summary table of COVID-19 associated treatment-emergent adverse events (TEAEs), including number and percentages of subjects as well as the number of events, will be provided for the Safety Analysis Set including for the following:

- Any TEAE (related/not related),
- Serious TEAE (related/not related),
- TEAE resulting in death (related/not related),
- TEAE leading to discontinuation of study treatment (related/not related),
- TEAE leading to study withdrawal (related/not related),
- TEAE by maximum severity (mild, moderate, severe, missing).

The following summary tables will be provided:

- TEAEs occurring within 7 days of COVID-19 vaccine administration by PT, Among Subjects Receiving COVID-19 Vaccination
- TEAEs excluding those occurring within 7 days of COVID-19 vaccine administration by PT.

The following listings of COVID-19 associated adverse events will be provided:

- Any AE,
- AEs within 7 days of COVID-19 vaccine administration.

Concomitant Medications

Concomitant medications used to treat COVID-19 associated adverse events will be flagged in the listing of prior and concomitant medications.

For concomitant medications which are linked to specific adverse events, the eCRF collects information to identify the specific adverse event (e.g., Adverse Event ID). As described in the Adverse Events section, relevant adverse events will be identified by the following Standardized MedDRA Query (SMQ): COVID-19 (SMQ).

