10.1.1 Primary Estimand

The primary interest is to assess the treatment effect of CSL312 during treatment from Day 1 through Day 182 while subjects are allowed to treat HAE attacks with on-demand medications.

The primary estimand in line with the primary interest of the study follows the treatment policy strategy and is described as follows:

- Treatment Condition: monthly treatment of CSL312 or placebo
- Population: the target patient population defined by eligibility criteria and who were randomized (ITT).
- Variable: time-normalized number of HAE attacks per month during treatment from Day 1 through Day 182.

Intercurrent events: The occurrence of an intercurrent event is irrelevant. All observed values will be used regardless of occurrence of any of the following intercurrent events:

- administration of on-demand medication in addition to prophylactic treatment with CSL312,
- Prohibited concomitant medications due or not due to COVID-19 or COVID-19 vaccination,
- non-compliance to treatment due or not due to COVID-19 or COVID-19 vaccination,
- early study discontinuation due or not due to COVID-19.

- Population-level summary: median time-normalized number of HAE attacks per month during treatment from Day 1 through Day 182 by treatment.

If a subject discontinued the study early after being continuously the first 30 days in the treatment period, the observation is terminated by the Early Termination Visit. It is assumed that the attack rate for subjects, who discontinued the study after the 30th study day and before the end of the 6th month, is comparable to the attack rate from subjects who have the entire 6 months treatment period observed. This assumption is based on CSL312_2001 data which showed that the CSL312 treatment effect was maintained over time. Therefore, the primary endpoint will be considered measurable and not missing, ie, the time-normalized number of HAE attacks will be calculated based on the HAE attacks reported until the Early Termination Visit.

In case a subject discontinues study treatment due or not due to COVID-19 but continues participation in the study for more than 30 days beyond the last study drug administration,

the HAE attacks until the last study drug administration plus 30 days will be included in the HAE attack analysis and length of subject treatment in days will be derived as:

[date of last study drug administration – the date of Study Visit Day 1 of the Treatment Period +31].

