11.2 Adverse Events

AEs will be coded using the MedDRA dictionary. Treatment-emergent AEs (TEAEs), defined as AEs starting on or after the date (and time if available) of the first study drug administration, will be summarized. All AEs regardless of whether they were treatment-emergent or not will be listed.

AEs with completely or partially missing date or time will be considered treatment-emergent following the worst-case principle, unless the partial date clearly indicates that the AE started before the first administration of study drug. AEs with completely missing start dates will be considered treatment-emergent. If only the day is missing, and the start month and year of the

AE is before the start month and year of the first administration of study drug, the AE will be considered non-treatment-emergent. If day and month are missing and the start year of the AE is before the year of the first administration of study drug, the AE will be considered non-treatment-emergent.

Summaries of TEAEs will count the number of subjects, that is, subjects with multiple occurrences of the same TEAE will be counted once in the total of those experiencing this PT. Similarly, a subject with 1 or more PT in a SOC will be counted once in the total of those experiencing PTs in that SOC.

Injection site reactions (ISRs) will be summarized by SOC and PT forming a virtual SOC “Injection Site Reactions”. To decide which PTs will be considered ISRs, CSL will be provided a list in Excel format of all PTs found in the data base. CSL will review this list and mark the PTs considered ISRs in a column of this Excel sheet. The PTs summarized as ISRs will also be reported in their original MedDRA SOC. For the “Any TEAE” entry, the ISR will be reported once; they will not be counted in both their original and virtual SOC. ISRs will be presented as first “SOC” following the “Any TEAE” entry. The MedDRA SOCs and PTs will be presented in descending frequency of the overall CSL312 category. Within the same frequency, SOCs and PTs will be ordered alphabetically.

Overview summaries of TEAEs will be provided by treatment arm and total summarizing:

- Any TEAEs;
 - TEAEs related to study drug;
 - TEAEs leading to study discontinuation;
 - TEAE temporally related (onset within 24h after start of study drug administration);
 - TEAEs by severity (Mild, Moderate, Severe);

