 - TEAEs by outcome (Death, Not Recovered or Not Resolved, Recovered or Resolved, Recovered or Resolved with Sequelae, Recovering or Resolving, Unknown);
 - TEAE identified as Injection Site Reaction (ISR);
 - ISRs related to study drug;
 - ISRs by severity;
- Any Serious TEAEs (SAEs);
 - SAEs related to study drug;
 - SAEs leading to study discontinuation;
 - SAE temporally related;
 - SAEs by severity (Mild, Moderate, Severe);
 - SAEs by outcome (Death, Not Recovered or Not Resolved, Recovered or Resolved, Recovered or Resolved with Sequelae, Recovering or Resolving, Unknown).

The following summary tables will be provided:

- All TEAEs by SOC and PT,
- All TEAEs leading to study discontinuation by SOC and PT,
- All TEAEs by severity and by SOC and PT,
- All TEAEs related to study drug by SOC and PT,
- All AESI by SOC and PT,
- All ISRs by SOC and PT,
- All SAEs by SOC and PT,
- All Non-serious TEAEs by SOC and PT,
- Laboratory Findings reported as AEs,
- All AEs caused by COVID-19 (see [Section 7.1](#)),
- TEAEs occurring 7 days of COVID-19 vaccine administration (see [Section 7.1](#)),
- All TEAEs excluding TEAEs occurring within 7 days of COVID-19 vaccine administration.

Summaries will include the number and percentage of subjects, the number of TEAEs, and the number of TEAEs per injection and per subject year (where applicable) derived as:

$$\text{TEAE rate per SC Injection (AERI)} = \frac{\text{Number of Events for particular SOC/PT}}{\text{Number of SC Injections}};$$

$$\text{and TEAE rate per Subject SC Year (AERS)} = \frac{\text{Number of Events for particular SOC/PT}}{\text{Subject SC years}}.$$

where subject SC years will be the sum of the time in years that subjects were exposed to study drug administered by SC injections derived as:

[date of Study Completion or date of study discontinuation [whatever is first] – the date of Study Visits Day 1 within Treatment Period +1] / 365.25.

All AEs (treatment-emergent and non treatment-emergent) will be listed including MedDRA SOC, PT and verbatim, AE start and end date:time, duration of AEs in days, intensity, serious status, relationship to study drug, outcome, action taken, and AE flags (TEAES, SAE, AESI, clinically significant laboratory finding, temporal relationship).

The following listings will be provided:

- All Non-TEAEs,
- All TEAEs,
- All TEAEs leading to study discontinuation,
- All TEAEs related to laboratory findings,
- All TEAEs caused by COVID-19,

- All SAEs,

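### Outside the COVID-19 overview, SAP 11.2 has no summary or dedicated listing of adverse events that led to stopping study drug

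*SAP*

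**What the plan says.** **Stopping drug and leaving the study are separate events.** Protocol 4.3.1 covers the first and 4.3.2 the second. Under 4.3.1, subjects who stop the drug "will be encouraged to remain in the study until Day 182 in order to collect study assessments", and SAP section 4 repeats this. SAP 10.1.1 expects such subjects: it gives a separate derivation of attack count and treatment length for anyone who stops the drug but "continues participation in the study for more than 30 days beyond the last study drug administration".

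**SAP 11.2 uses only the second event.** The TEAE overview has a row for "TEAEs leading to study discontinuation" and its serious-event block a row for "SAEs leading to study discontinuation". The SOC/PT table is "All TEAEs leading to study discontinuation by SOC and PT", and the dedicated listing uses the same criterion.

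**SAP 7.1 uses both.** The overview of COVID-19-associated TEAEs has a row for "TEAE leading to discontinuation of study treatment (related/not related") and a separate row for study withdrawal.

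**The protocol is mixed.** In Protocol 10.3.3, the AE overview, the SAE overview and the listing all refer to study discontinuation. The SOC/PT table is "Incidence of subjects with AEs leading to discontinuation by SOC and PT", without saying discontinuation of what.

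**The concern.** Adverse events that lead to stopping the drug are a standard measure of tolerability, and evaluating safety is the second of the two secondary objectives. The planned discontinuation outputs count such an event only if the subject also leaves the study, which is what the protocol asks subjects not to do. The better sites are at retention, the fewer events these outputs capture.

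What is at stake is a by-arm statement of which events caused subjects to stop CSL312 or placebo, with their relatedness and seriousness. A reader of the study report would have to assemble it from subject listings.

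**Working it through.** The plan gives no figure to reproduce. The check is a comparison of texts, followed by simple arithmetic for scale.

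**Step 1. Criterion used by each output**

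| Output | Protocol 10.3.3 | SAP 11.2 | SAP 7.1 (COVID-19 events only) |
|---|---|---|---|
| AE/TEAE overview row | study | study | treatment and study, separately |
| SAE overview row | study | study | none |
| SOC/PT table | not specified | study | none |
| Listing | study | study | none by discontinuation |

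The one protocol output left open, the SOC/PT table, became study discontinuation in the SAP. SAP section 5 does not mention this and says there are no further changes to the planned analyses.

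**Step 2. Trace one hypothetical subject.** Suppose a subject on CSL312 stops the drug for a non-serious injection site reaction and stays to Day 182.

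- SAP 11.2 tables of all TEAEs, TEAEs by severity, injection site reactions and, if so judged, related TEAEs: the event is counted, with nothing to show that it stopped the drug.
- SAP 11.2 discontinuation row, SOC/PT table and listing: not included, because the subject did not leave the study.
- SAP 7.1 overview: not included, because the event is not associated with COVID-19.
- SAP 9.1 disposition table: counted as a premature treatment discontinuation with a reason, but without event term, relatedness or severity.
- SAP 11.2 listing of all AEs: shown with action taken. SAP 9.1 disposition listing: shown with the reason for stopping treatment.

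The link between the event and the stop therefore exists only in subject-level listings. Had the same subject stopped because of a COVID-19-associated event, SAP 7.1 would have counted it in a summary row, by relatedness.

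**Step 3. Scale.** SAP 4.5 (justification for Japanese subjects) gives planned arms of 36 on CSL312 and 24 on placebo. If k subjects in an arm stop the drug for an adverse event and stay in the study, the percentage with an event leading to a drug stop exceeds the percentage with an event leading to study exit by at least 100 × k / n points. The documents give no value for k, so the range below is an assumption.

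| k | CSL312 (n = 36) | Placebo (n = 24) |
|---|---|---|
| 1 | 1/36 = 2.8 points | 1/24 = 4.2 points |
| 2 | 2/36 = 5.6 points | 2/24 = 8.3 points |
| 3 | 3/36 = 8.3 points | 3/24 = 12.5 points |

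The actual denominators will be the Safety Analysis Set by treatment received and may differ slightly.

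**The case against.** The strongest reply is that the SAP mostly follows the protocol. Three of the four protocol outputs already say study discontinuation, and the bare word in the fourth can be read as shorthand for the same thing. That stands. A reader might infer that the SAP contradicts the protocol, but the texts support only a narrowing of one ambiguous table without comment.

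The second reply is that the information is already planned. In a trial of about 60 subjects, the few relevant cases can be found from the listings of action taken and of the reason for stopping treatment. Thromboembolic, bleeding and severe hypersensitivity events fall under the AESI table, and injection site reactions have their own table and overview rows. This also stands, and it limits the loss to the summary-level link between event and drug stop. It does not supply that link: none of these tables shows by arm which events stopped treatment.

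The third reply is that the number may be very small. Protocol 1.2.3.1 reports no withdrawals due to adverse events in phase 1, and 1.2.3.2 reports no SAEs or AESIs in the interim phase 2 results. That does not establish a rate for this trial, but nothing in the documents supports a large one either.

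**Conclusion.** The point holds in a narrow form, as a cheap improvement to safety reporting. Outside the COVID-19 overview, no by-arm adverse event summary in the SAP identifies events that led to stopping study drug, although the plan encourages subjects who stop to remain and has an efficacy rule for them.

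Two stronger readings are not supported. A reader might infer that these events vanish from the safety tables; they do not, as the trace shows. A reader might also infer that the planned discontinuation percentage would be wrong; it would be right for its label, and a zero there would be a true zero for study exits. The risk is that it is taken as a measure of drug stops, with no such measure beside it.

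The size is 2.8 points per subject on CSL312 and 4.2 on placebo, with an unknown number of subjects. The protocol only encourages staying, so some who stop the drug for an adverse event will also leave and will be counted. Nothing here touches the primary analysis, the hierarchical tests, power or alpha.

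The conclusion assumes that the separate table shells, which are not part of the documents, do not already contain these outputs. The remarks on the disposition table assume that adverse event is among the reasons on the eCRF.

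**What to change.** In SAP 11.2, add TEAEs leading to discontinuation of study treatment, using the SAP 7.1 criterion, in three places beside the existing study-discontinuation outputs:

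- the overview, with rows for any, related and serious events;
- the SOC/PT tables;
- the listings.

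State which meaning the protocol's SOC/PT discontinuation table carries, and record that choice in SAP section 5.

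Derive the flag from the action-taken field already planned for the AE listing, checked against the End of Treatment form named in SAP 7.1. Since SAP 7.1 needs the same derivation for COVID-19 events, the data should support it for all events; confirm this against the eCRF.

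The cost is a few more table rows and a listing, with no new data collection. The downside for the sponsor is that the reported tolerability figure may be less favourable.

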11.3 Clinical Laboratory Evaluations

Laboratory tests will be summarized descriptively by scheduled visit and treatment arm. For laboratory tests with continuous values, descriptive statistics for the measured values and for change from baseline will be presented. Definition of the baseline assessment can be found in [Section 8.2.3](#). Laboratory tests with categorical values will be summarized by number and percentage of subjects in the respective categories (based on subjects of the Safety Analysis Set with non-missing values at this Study Visit). Summary tables will be provided for hematology, biochemistry, coagulation, and immunogenicity (binding antibodies: inhibitory and non-inhibitory; specific to FXIIa inhibitor monoclonal antibody, anti-CSL312) and urinalysis. All laboratory test results (scheduled and unscheduled) will be listed.

The listings will include test name and unit along with normal range, the sampling date and time, the test result, an assessment whether the result is high (above normal range) or low (below normal range). Any comments to the laboratory test will be provided in a separate listing, if applicable.

A by-subject listing for laboratory abnormalities will be provided in the same format as the laboratory listings described above but only containing information about abnormal laboratory results.

The laboratory tests will be presented in the following grouping and sequence as specified in Table 4 of the CSP. The test names used in the TFL outputs may differ depending on the terminology used by the central laboratory. The test names and units as provided in the laboratory data transfer will be used.

The number and percentage of subjects with clinically significant laboratory findings related to an TEAE will be summarized by laboratory test. Those will be identified through the eCRF form 'Clinical Significant Safety Lab Data.' Percentages will be based on subjects in the Safety Analysis Set with non-missing values at each Study Visit.

11.4 Other Safety Measures

11.4.1 Vital Signs

Systolic and diastolic blood pressure, respiratory rate, pulse rate, temperature, height, and body weight will be collected as vital signs.

Vital Signs will be presented in standard units and in alphabetical order. Summaries to be produced will be:

- descriptive statistics for vital signs at each scheduled visit and change from baseline (visit value – baseline value).

Listings to be produced are:

- vital signs results and change from baseline by nominal visit, visit date and time.

11.4.2 ECG

All ECG findings will be summarized by treatment arm and listed by subject including nominal visits, assessment date and time, clinically significant and abnormal status (Yes, No) and related AE ID.

11.4.3 Physical Examination

Date and time of performed physical examinations will be listed only.

12 Pharmacokinetic Analyses

Plasma samples for CSL312 concentrations will be collected during Treatment Period at the following study visits: Day 1, Day 31, Day 61, Day 91, Day 121, Day 151, Day 182 and Day 242 (if applicable).

All analyses in this section will be based on the PK Analysis Set and will be only conducted for subjects treated with CSL312.

12.1 Drug Concentration Measures

The summaries will be given by nominal time points (planned time points) with descriptive statistics: mean, SD, percent coefficient of variation, median, minimum, maximum, and first and third quartiles for continuous variables, geometric mean and its respective 90% CI.

The geometric coefficient of variation will be expressed as a percentage and will be calculated as $100 * \sqrt{\exp(\text{SD}_{\log}^2) - 1}$. The geometric mean and its 90% CI will be calculated by log-transforming the data, calculating the mean and the lower and upper limits of the 90% Wald CI of the log-transformed data, and subsequently back transforming the mean and the lower and upper limits.

The summaries for CSL312 concentrations will be also stratified according to the following:

- Age (adolescent [12 to ≤ 17 years] and adult [>17 years] subjects),
- Region (Japanese and non-Japanese subjects).

Below lower Limit of Quantification (BLQ) of CSL312 plasma concentrations will be handled as follows:

- pre-dose BLQ results (prior first study drug administration) will be treated as zero;
- all other post-dose BLQ results will be set to missing.

If in total more than 50% of the values at a nominal time point are imputed (i.e., BLQ) or missing, then the summary statistics will not be displayed.

Mean (\pm SD) CSL312 concentrations versus nominal time point will be plotted on linear and semi-logarithmic scales.

All concentrations results will be listed by subject, including actual sampling date and time, nominal time point and actual time from end of previous injection. BLQ results will be listed as "BLQ".

13 Pharmacodynamic and Biomarkers Analyses

All analyses in this section will be based on PD Analysis Set.

